## 3.9.2.3 Height and Weight

Height, in centimeters, should be measured when the subject's shoes are off, feet together, and arms by the sides. Heels, buttocks, and upper back should also be in contact with the wall when the measurement is made.

Body weight, in kilograms, should be obtained with the subject wearing undergarments or very light clothing and no shoes, and with an empty bladder. The floor surface on which the scale rests must be hard and should not be carpeted or covered with other soft material. The same scale should be used throughout the study and calibrated on a regular basis as recommended by the manufacturer.

The body mass index (BMI) value will be calculated based on the height and weight.

#### 3.9.2.4 Vital Signs

Vital signs may include body temperature, respiratory rate, pulse, and sitting systolic and diastolic blood pressures, as deemed appropriate by investigator.

### 3.9.2.5 Pulmonary Function Tests

Subjects will undergo FEV1 testing according to American Thoracic Society and European Respiratory Society recommendations in the clinic. Subjects who experience respiratory symptoms that are not associated with an upper respiratory infection (URI) should undergo additional pulmonary function test to monitor clinically relevant decline (Section 4.1.3) per investigator's discretion in accordance with the Afrezza USPI. FEV1 values will be recorded in the CRF

Confidential Page 54 of 70

### 3.9.2.6 Hypoglycemic Events

A hypoglycemic episode is defined as any event with SMBG <70 mg/dL (i.e., Level 1 hypoglycemia) or SMBG <54 mg/dL (i.e., Level 2 hypoglycemia) (ADA 2021a) on the study-provided glucose meter. Severe hypoglycemic events are defined as events requiring assistance of another person to actively administer carbohydrate, glucagon, or other resuscitative actions. Severe hypoglycemic events will be documented as SAEs in the CRF. Nonsevere hypoglycemic events will not be documented as AEs but will be recorded in the hypoglycemia page of the CRF.

After the standardized meal challenge at Visit 2, subjects will be monitored for signs of hypoglycemia. Subjects exhibiting signs of hypoglycemia will be treated as appropriate (e.g., provided with a snack or glucose). The type of treatment given and time will be recorded and subjects will remain in-clinic until hypoglycemia is resolved.

In the event that the subject accidentally enters carb intake/meal announcement for a certain meal and also doses with Afrezza, carbohydrates or glucagon should be administered. The subject should be instructed to contact the Investigator and site staff as soon as possible following the event to ensure prompt review and to give the Investigator the opportunity to address any further necessary measures for correction.

## 3.9.2.7 Hyperglycemic Events and Diabetic Ketoacidosis (DKA)

Investigators will educate subjects on recognizing and managing hyperglycemia and DKA using their CGM and study provided glucose meter, taking additional insulin and/or checking ketones as required. To ensure subject safety, subjects will be removed from the study if they have two events of DKA. Events of DKA are considered AESIs (Section 4.1.3) for which diagnostic criteria in Section 4.1.3.1 must be met.

At the time of suspected DKA accompanied by a CGM value of >250 mg/dL, the subject's blood glucose should be measured using the study-provided glucose meter to confirm.

- If glucose is > 250 mg/dL for more than 4 consecutive hours and continues >250 mg/dL after the subject has taken insulin and ingested water, ketones should be measured. If serum ketones are >1.5mmol/L or urine ketones are "moderate" or greater, the subject should contact the site staff and/or their physician as soon as possible for further guidance and ketones should be tested every hour until serum ketones are <1.5mmol/L or urine ketones are less than "moderate". Symptoms should be treated in accordance with standard of care instructions from the Investigator.
- If glucose is > 250 mg/dL and the subject is vomiting or feels ill, ketones should be measured. If serum ketones are >1.5mmol/L or urine ketones are "moderate" or greater, the subject should contact the site staff and/or their physician as soon as possible for further guidance and ketones should be tested every hour until serum ketones are

Confidential Page 55 of 70

<1.5mmol/L or urine ketones are less than "moderate". Symptoms should be treated in accordance with standard of care instructions from the Investigator.

## 3.9.2.8 Clinical Laboratory Tests

The clinical site will collect blood samples for HbA1c, creatinine and TSH from subjects at Visit 1. Samples for HbA1c will be forwarded to the central laboratory for analysis. Samples for creatinine and TSH will be tested by a local laboratory; however, a documented normal TSH or creatinine within 6 months of screening can be used in lieu of testing. Urine pregnancy tests (for β-human chorionic gonadotropin) will be performed locally for women of child-bearing potential only.

### 3.9.2.9 Adverse Events

All AEs occurring after enrollment and through the duration of the study will be recorded. See Section 4 for additional information.

## 3.9.3 Appropriateness of Measurements

All assessments to be used in this study are commonly used and generally recognized as relevant in diabetes studies.

Confidential Page 56 of 70

#### 4 ADVERSE EVENT REPORTING

Throughout the course of the study, all AEs will be monitored and recorded in an AE page of the CRF, including the AE's description, start and end date, seriousness, severity, action taken, and relationship to the study drug. If AEs occur, the first concern will be the safety of the study subjects. All AEs will be followed until resolved or stable and the outcome documented in the CRF.

#### 4.1 Definitions and Criteria

### 4.1.1 Adverse Events

Per ICH E2A, an AE is any untoward medical occurrence in a subject or clinical investigation subject administered a pharmaceutical product and which does not necessarily have to have a causal relationship with this treatment. An AE can therefore be any unfavorable and unintended sign (including an abnormal laboratory finding, for example), symptom, or disease temporally associated with the use of a medicinal product, whether or not considered related to the medicinal product.

The intensity of each AE will be determined according to the following criteria:

- Mild: no modification of daily activities and does not require corrective/symptomatic treatment.
- Moderate: hinders normal daily activities and/or requires corrective/symptomatic treatment.
- Severe: prevents daily activities and requires corrective/symptomatic treatment.

Medical interventions such as surgeries, diagnostic procedures, and therapeutic procedures are not AEs, but the action taken to treat a particular medical condition. They should be recorded as treatment of the AEs.

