#### 4.1.2 Serious Adverse Events

An SAE or reaction is any untoward medical occurrence that:

- Results in death
- Is life-threatening
- Requires inpatient hospitalization or prolongation of existing hospitalization
- Results in persistent or significant disability or incapacity
- Is a congenital anomaly or birth defect
- Is an important medical event (e.g., intensive treatment in an emergency room or at home for allergic bronchospasm; blood dyscrasias, or convulsions that do not result in hospitalization; or development of drug dependency or drug abuse; malignancy tumors [histologically different from primary tumor])

Medical and scientific judgment should be exercised in deciding whether expedited reporting is appropriate in other situations, such as important medical events that may not be immediately life-threatening or result in death or hospitalization but may jeopardize the subject or may require intervention to prevent one of the other outcomes listed in the definition above.

Confidential Page 57 of 70

Seriousness (not severity) serves as a guide for defining regulatory reporting obligations. An SAE is not necessarily severe. Similarly, a severe AE is not necessarily serious (e.g., nausea of several hours' duration may be rated as severe but may not be considered serious).

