### 5.4.1 Safety Endpoints

- Event rates and incidence Level 1 (<70 mg/dL) and Level 2 (<54 mg/dL) hypoglycemic events as confirmed by SMBG
- Event rates and incidence of severe hypoglycemic events, defined as events requiring assistance of another person to actively administer carbohydrate, glucagon, or other resuscitative actions
- Incidence and severity of AEs: TEAEs, SAEs, AESIs, and device complaints
- Change in FEV1 from screening to end of study

Confidential Page 62 of 70

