### 5.15 Descriptive Summary of Safety

The incidence of hypoglycemia (total, nocturnal, and severe) and percentage time below 70 mg/dL and below 54 mg/dL will be reported. Nocturnal is defined as midnight to 0600 and severe hypoglycemia is defined as an event requiring assistance of another person to actively administer carbohydrate, glucagon, or other resuscitative actions.

The number and percentage of subjects with treatment-emergent AEs will be tabulated by system organ class and preferred term by relationship to treatment and by severity.

A summary table by study visit with descriptive statistics for  $FEV_1$  at screening and end of study will be provided. The  $FEV_1$  data will also be presented graphically.

Confidential Page 64 of 70

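### The AE intensity scale cannot grade as Severe an event that prevents daily activities but requires no treatment, and events that do both fit two grades

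*Protocol*

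**What the plan says.** Section 4.1.1 of the protocol introduces the scale with "The intensity of each AE will be determined according to the following criteria", so it covers every AE. There are three grades:

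- The lowest needs both of its conditions to hold: "Mild: no modification of daily activities and does not require corrective/symptomatic treatment".
- For the middle grade, either condition is enough: "Moderate: hinders normal daily activities and/or requires corrective/symptomatic treatment".
- The highest again needs both: "Severe: prevents daily activities and requires corrective/symptomatic treatment".

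Section 4.2.1 sends the investigator back to Section 4.1.1 for the intensity of each recorded event. Section 5.4.1 makes severity a safety endpoint: "Incidence and severity of AEs: TEAEs, SAEs, AESIs, and device complaints". Protocol Section 5.15 then tabulates subjects with treatment-emergent AEs "by system organ class and preferred term by relationship to treatment and by severity", and SAP Section 8.2.4 plans the same tables. Neither document gives a second scale, a rule to take the highest grade met, or any other tie-break.

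Section 4.1.2, in separating seriousness from severity, remarks that "nausea of several hours' duration may be rated as severe but may not be considered serious". It does not mention treatment.

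**The concern.** The scale rests on two attributes: how far the event interferes with daily activities, and whether it requires treatment. The connecting word changes between grades. Either attribute is enough for Moderate, but Severe demands both. An event can therefore reach the worst level of activity impact and still be kept out of the top grade because it requires no treatment.

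At stake is the severity column of the AE tables. An event that stops a subject's normal day but needs no remedy would be recorded one grade lower, or two investigators could treat it differently, one grading it Moderate and the other finding no grade that fits.

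**Working it through.** The plan gives no figure to reproduce here. The check is whether the three definitions give every event exactly one grade.

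**Inputs.** Activity impact has three levels (none, hinders, prevents) and treatment required has two (no, yes), so there are 3 × 2 = 6 combinations. The grading rules are those of Section 4.1.1. Because the text does not say whether preventing activities is also a form of hindering them, each combination was graded under both readings.

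| Activity impact | Treatment required | Prevents counts as hinders | Prevents does not count as hinders |
|---|---|---|---|
| None | No | Mild | Mild |
| None | Yes | Moderate | Moderate |
| Hinders | No | Moderate | Moderate |
| Hinders | Yes | Moderate | Moderate |
| Prevents | No | Moderate | no grade |
| Prevents | Yes | Moderate and Severe | Moderate and Severe |

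**Result.** Four of the six combinations get exactly one grade under either reading. The two that fail are the two in which activities are prevented:

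- *Prevents, no treatment required.* Severe is out because its second condition fails. Mild is out because activities are modified. What remains is Moderate or nothing, depending on the reading.
- *Prevents, treatment required.* Severe is met. Moderate is met as well, because requiring treatment satisfies it alone.

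**Direction.** For the first type, the recorded grade is below Severe or absent. It cannot be too high.

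**Scale of one change.** The planned arms are 10, 10 and 5 subjects (protocol Section 3.1). If one subject's only candidate event moves into or out of Severe, the percentage with a severe AE changes by 1/10 = 10 points in an Afrezza arm or 1/5 = 20 points in AID Control. That is simply the weight of one subject in any table of this size. It is not an estimate of how often the problem arises, and it does not apply to a subject who has another severe AE.

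**Frequency.** The documents give no AE rates, so the number of affected events cannot be computed.

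**The case against.** The best defence is that the scale works in practice. On an ordered scale, an investigator would naturally assign the highest grade that is fully met, so the overlap between Moderate and Severe would rarely matter. In ordinary language, an event that prevents activities also hinders them, so the other combination would be graded Moderate rather than left blank. A sponsor may also choose to reserve Severe for events that both incapacitate and need treatment. The nausea remark in Section 4.1.2 does not decide the matter, because it is silent on whether that nausea required treatment.

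Much of this stands. It reduces the problem to a single combination in practice, but it depends on a convention and a reading that neither document states. Activity impact also rises from grade to grade within the scale itself, so holding the highest level of impact at Moderate runs against the scale's own order.

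Three stronger readings are tempting, and the documents do not support them.

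- A reader might infer that any incapacitating event left *untreated* is downgraded. The criterion is that treatment is required, not that it was received. An incapacitating event that needed treatment and got none still meets Severe.
- A reader might infer that, because the trial is open-label, differences between arms in treatment given would feed into the grades. That fails for the same reason. Judgement of need could in principle differ by arm, but nothing in the documents shows that it does.
- A reader might infer that severity *is* understated. Only the direction can be established. The amount is unknown.

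**Conclusion.** The scale is wrong as written, in a minor way. An event that prevents daily activities without requiring treatment cannot be Severe, and one that does both fits two grades with no rule to choose. Two of six combinations are affected. That is a count of logical cases and says nothing about the share of events, since the six are not equally likely.

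The consequence is confined to the descriptive tabulation of AE severity. Section 4.1.2 ties reporting duties to seriousness, and AESIs are listed in Section 4.1.3 whatever their intensity. Severe hypoglycemia has its own definition and is recorded as an SAE under Section 3.9.2.6. The sponsor's stopping criteria in Section 6.1.5 do not use intensity grades. No significance testing is planned (Section 5.6).

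The conclusion assumes that no CRF instruction outside these documents already supplies a tie-break or a fuller definition of Severe. The CRF is not among the documents, and the data management sections of the SAP are redacted.

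**What to change.** In Section 4.1.1, keep Mild and reword the other two grades along these lines:

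- **Moderate:** does not prevent daily activities, but hinders them and/or requires corrective/symptomatic treatment.
- **Severe:** prevents daily activities, whether or not corrective/symptomatic treatment is required.

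In the order of the table above, the six combinations then become Mild, Moderate, Moderate, Moderate, Severe and Severe, with one grade each. Use the same wording in the AE CRF instructions.

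Two lighter edits would not be enough. Attaching the exclusion only to the hindering clause of Moderate leaves the overlap, because an incapacitating event that requires treatment would still qualify through the treatment clause. Adding only a highest-grade rule resolves the overlap but leaves the incapacitating event that requires no treatment outside Severe.

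The cost is a small edit to the protocol and the matching CRF text. The count of severe events may turn out slightly less favourable. No analysis or sample size changes.

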#### 4.1.2 Serious Adverse Events

An SAE or reaction is any untoward medical occurrence that:

- Results in death
- Is life-threatening
- Requires inpatient hospitalization or prolongation of existing hospitalization
- Results in persistent or significant disability or incapacity
- Is a congenital anomaly or birth defect
- Is an important medical event (e.g., intensive treatment in an emergency room or at home for allergic bronchospasm; blood dyscrasias, or convulsions that do not result in hospitalization; or development of drug dependency or drug abuse; malignancy tumors [histologically different from primary tumor])

Medical and scientific judgment should be exercised in deciding whether expedited reporting is appropriate in other situations, such as important medical events that may not be immediately life-threatening or result in death or hospitalization but may jeopardize the subject or may require intervention to prevent one of the other outcomes listed in the definition above.

Confidential Page 57 of 70

Seriousness (not severity) serves as a guide for defining regulatory reporting obligations. An SAE is not necessarily severe. Similarly, a severe AE is not necessarily serious (e.g., nausea of several hours' duration may be rated as severe but may not be considered serious).

## 4.1.3 Adverse Events of Special Interest

An adverse event of special interest (AESI) is an AE (serious or nonserious) of scientific and medical concern, specific to the investigational medicinal product or program, for which ongoing monitoring and rapid communication by the Investigator to the Sponsor may be appropriate. Such events may require further investigation in order to characterize and understand them.

For AESIs, the Sponsor must be informed immediately (i.e., within 24 hours), per the SAE notification guidelines described in Section 4.2.3.

The following AEs are considered AESIs:

- Acute bronchospasm
- Clinically relevant decline in pulmonary function (>20% decline from baseline percent predicted FEV1 OR respiratory symptoms not associated with URI
- Hypersensitivity reactions, including anaphylaxis, which can occur with insulin products, including Afrezza
- DKA

### 4.1.3.1 Diagnostic Criteria for Diabetic Ketoacidosis

The following diagnostic criteria must be met to be considered a DKA event (ADA 2004):

- Arterial blood pH <7.30 or serum bicarbonate <15 mEq/L

- Blood glucose >250 mg/dL (or >13.9 mmol/L)
- Serum ketones or large/moderate urine ketones
- Symptoms such as polyuria, polydipsia, nausea, or vomiting
- Treatment provided in a health care facility

### 4.1.4 Abnormal Laboratory Values

Any abnormality in a laboratory value that is new in onset or that has worsened in severity or frequency from the baseline condition and meets one of the following criteria will be recorded in the AE pages of the CRF:

- Requires therapeutic intervention or diagnostic tests
- Leads to discontinuation of study drug
- Has accompanying or inducing symptoms or signs
- Is judged by the Investigator as clinically significant

### 4.1.5 Assessing Relationship

The Investigator will classify every AE according to its relationship to study drug, study device, or study-related procedure. The AE relationship categories that will be used are listed below:

#### **Related:**

An AE that occurs at a reasonable time interval after administration of the investigational

Confidential Page 58 of 70

product, use of the device, or procedure

- An AE that follows a known response pattern to the investigational product, use of the device, or procedure
- An AE that improves after stopping the investigational product, use of the device, or
  procedure and reappears after repeated exposure to the investigational product, device, or
  procedure. Depending on the nature of the AE, rechallenge may not be possible.

## **Probably related:**

- An AE that occurs at a reasonable time interval after administration of the investigational product, use of the device, or procedure
- An AE that follows a known response pattern to the investigational product, use of the
  device, or procedure, where an alternative explanation (e.g., a concomitant drug or
  concurrent disease) is less likely

### Possibly related:

- An AE that occurs at a reasonable time interval after administration of the investigational product, use of the device, or procedure
- An AE that follows a known response pattern to the investigational product, use of the
  device, or procedure, but could have been produced by the subject's clinical status or by
  other therapies

## **Unlikely related:**

- An AE for which sufficient information exists to indicate that the etiology is unrelated to the investigational product, use of the device, or procedure
- An AE for which another etiology is specified

#### Not related:

- An AE without a temporal relationship to the investigational product (e.g., an AE occurring in a subject who has not received investigational product), use of the device, or procedure
- An AE for which another cause is known

### 4.2 Reporting Procedures and Requirements

### **4.2.1** Adverse Events

Any AEs occurring from the date that the subject consents to participate in the study until they exit the study will be recorded.

The Investigator should document all AEs in the subjects' source documentation, on the AE CRF, and the SAE report (if the AE is serious). AEs of hypoglycemia that meet SAE criteria should be documented in the AE CRF and SAE report.

The Investigator should specify the date of the onset of the AE, the intensity (see definitions in Section 4.1.1), action taken with respect to the study drug, corrective treatment/therapy given, additional investigations performed, outcome, and the relationship to study drug (Section 4.1.5)

Confidential Page 59 of 70

Whenever possible, the diagnosis or syndrome should be reported instead of individual associated symptoms (e.g., record "influenza" if this is the diagnosis instead of "fever" and "chills").

Every AE and serious AE should be followed until resolved, or resolved with sequelae, or considered stable in the opinion of the Investigator. To the extent possible, event resolution information will be obtained by means of due diligence (see the site operations manual).

If the severity of an AE increases, a new AE CRF must be completed for that AE. The date of change would be included as the end date for the original AE and the start date for the new AE of greater severity.

